1.8 STUDY ANALYSIS SETS

1.8.1 INTENT TO TREAT ANALYSIS SET (ITT)

All subjects randomized will be included in the intent-to-treat (ITT) Analysis Set. The ITT analysis will only be considered a supportive and complementary analysis.

1.8.2 MODIFIED INTENT TO TREAT ANALYSIS SET (mITT)

For the primary analysis and safety evaluations, the mITT Analysis Set will be defined and presented as primary. The mITT Analysis Set includes all enrolled subjects who actually receive the device. If all enrolled subjects receive the device, the mITT and ITT Analysis Sets will coincide and will be referred to as the ITT Analysis Set.

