11.3 PRE-TREATMENT DEVICE USE ONBOARDING

Participants in the EaseVRx and Sham VR conditions will receive a PICO G2 4K headset with either EaseVRx or Sham content along with detailed instructions that will help them familiarize themselves with the hardware and software components. Telephonic and email technical support from study staff will be available to advise participants having trouble using the equipment. The participant will receive a reminder email to confirm VR headset receipt within 48 hours after FedEx tracking number was sent.

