16 SAFETY REPORTING

Participants will be carefully monitored during the study for possible adverse events (AEs) from the time they start treatment or sham to the time of study completion. All medical events and conditions prior to

this time point are to be captured as medical history. Any observed AE will be fully investigated by the Investigator and classified in line with the definitions below.

All adverse events that occur during this study will be recorded on the adverse event eCRFs and must include the following information at minimum:

- Event Description
- Date of Onset
- Date of Resolution
- Severity
- Seriousness
- Relationship to Study Device/Procedure
- Outcome

Adverse events will be recorded and classified by the research team, including a medical doctor on staff, using the specific signs, symptoms, or medical diagnosis if no signs or symptoms can be identified.

Significant new information and updates should continue to be captured in the participant's records and in the EDC as they become available and the adverse event should be followed until it is resolved or no further improvement is expected, or the participant is lost to follow-up. The Investigator will record all AEs regardless of whether they are anticipated or unanticipated and regardless of classification, seriousness, intensity, outcome, or causality.

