16.4 ADVERSE EVENT REPORTING

The collection of AEs will begin as soon as the participant first puts on the VR headset for this study. All AEs that occur through completion of the final follow-up visit, whether or not thought to be device related, should be recorded in detail and followed to resolution.

The description of the AE will include the date and time of onset, severity, relationship to the use of the device, the results of any diagnostic procedures or laboratory tests, if any treatment was required, and the outcome of the event. The AVR research team will follow each participant who experiences an AE until the event resolves, resolves with sequelae, or no further improvement is expected. In the unusual circumstance that an AE has not resolved by the time the participant completes the study, an explanation will be entered in the study database.

Note: Any condition at baseline that is recorded as a preexisting condition is not an AE unless it worsens in intensity or duration.

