3.2 SAFETY ANALYSIS

Assessment of the safety of the investigational device will include an evaluation of the incidence and severity of complications and adverse reactions associated with the treatment. Primary safety comparisons will be performed using the mITT analysis set.

Adverse event rates will be summarized by type of AE and for specific AEs in two ways:

1. Per subject incidence of specific AEs and classes of AEs
2. By event, summarizing event counts by visit interval over time and in accordance with FDA Guidance (CDRH 2004).

Events will be summarized by severity and relatedness.

The summary tables will show the adverse events (in coded terms), the total number of events, and the number and the percentage of subjects affected in the investigational group

(“subject wise evaluation”) and stratified by relation to device and severity. Data of dropouts will not be presented separately, but possible bias will be discussed in the final report.

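### Per-subject adverse event incidence is taken over everyone who received a headset, although adverse events are collected only from first wear

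*SAP*

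**What the plan says.** **Who is in the safety denominator.** SAP 1.8.2: "For the primary analysis and safety evaluations, the mITT Analysis Set will be defined and presented as primary". The same section defines the set: "The mITT Analysis Set includes all enrolled subjects who actually receive the device". SAP 3.2 repeats the choice: "Primary safety comparisons will be performed using the mITT analysis set".

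**What receipt means.** Protocol 11.3 treats it as courier delivery: a reminder email asks the participant to "confirm VR headset receipt within 48 hours after FedEx tracking number was sent". Wearing the headset is a separate, later event.

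**When AEs are collected.** Protocol 16 monitors participants for AEs "from the time they start treatment or sham to the time of study completion". Protocol 16.4 is more specific: "The collection of AEs will begin as soon as the participant first puts on the VR headset for this study". From then on all AEs are recorded, whether or not they are thought to be device related.

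**How AEs are summarised.** SAP 3.2 names two forms. The first has a denominator: "Per subject incidence of specific AEs and classes of AEs". The second does not: "By event, summarizing event counts by visit interval over time".

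**What is absent.** SAP 1.8 defines no set of participants who used the device at least once. Its only use-based set is Per Protocol (SAP 1.8.3, 42% threshold), which is planned for the primary and selected secondary endpoints and not for safety.

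**The concern.** The denominator starts at delivery and the numerator starts at first wear. Someone who receives the headset and never puts it on is reported as a participant without an AE. For device-caused events that person was never at risk. For unrelated events the person may have had one, but no collection period was ever opened.

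The trial mails the device to the home for self-administered, unsupervised use, so some non-use after delivery is plausible. At stake are the absolute AE percentages that describe the device's tolerability. They can be understated but not overstated by this route, and no analysis in the SAP would show by how much.

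**Working it through.** The documents state no AE incidence for this trial, no safety denominator and no never-use rate, so there is no figure of theirs to reproduce. The size follows from algebra and a labelled assumption.

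**Inputs**
- N, recipients per pooled group: about 500. Protocol 6.1 plans about 1000 participants at 1:1:1:1, so 1000 / 2 = 500 for EaseVRx and 500 for Sham, taking all as recipients.
- p, incidence among users: 10% and 20%, for illustration. Protocol 7.7.1 reports less than 10% for cybersickness that prevented use in previous research, so 10% is a convenient reference and not a forecast.
- u, never-use share: **assumed** 1% to 15%. The top of the range borrows the 15% loss-to-follow-up rate in SAP 2.8.1 as an outer limit only; it is not a never-use rate.

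**Dilution of one group's incidence**

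Users = N(1 - u). Users with an event = N(1 - u)p. Never-users with an event = 0.

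Reported incidence = N(1 - u)p / N = (1 - u)p.

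| u (assumed) | Never-users of 500 | p = 10% shown as | p = 20% shown as |
|---|---|---|---|
| 1% | 5 | 9.9% | 19.8% |
| 2% | 10 | 9.8% | 19.6% |
| 5% | 25 | 9.5% | 19.0% |
| 10% | 50 | 9.0% | 18.0% |
| 15% | 75 | 8.5% | 17.0% |

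At u = 0 the two denominators coincide.

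**Between-arm comparison, equal never-use**

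The factor (1 - u) cancels in the ratio and multiplies the difference. For 10% against 5% among users and u = 5%: 9.5% / 4.75% = 2.0, unchanged; 9.5 - 4.75 = 4.75 points instead of 5.

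**Between-arm comparison, unequal never-use (assumed splits)**

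The ratio is multiplied by (1 - u for EaseVRx) / (1 - u for Sham). With the same 10% among users in both arms:
- 2% never-use in EaseVRx, 10% in Sham: 9.8 / 9.0 = 1.09.
- 10% in EaseVRx, 2% in Sham: 9.0 / 9.8 = 0.92.

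The difference also loses its fixed direction. With 10% against 5% among users, the first split gives 9.8 - 4.5 = 5.3 points and the second 9.0 - 4.9 = 4.1 points, where the value among users is 5.

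**An event never observed**

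The exact one-sided 95% upper bound is 1 - 0.05^(1/n). On n = 500 recipients it is 0.60%. On actual users it is 0.63% (n = 475, u = 5%), 0.66% (n = 450, u = 10%) and 0.70% (n = 425, u = 15%).

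**The case against.** **The effect is small.** At 10% on 500 participants the standard error is sqrt(0.10 x 0.90 / 500) = 1.3 points, so a 95% interval is about +/- 2.6 points. The shift at u = 5% to 10% is 0.5 to 1.0 point, and the documents contain no safety decision rule that it would change. This stands and limits the point to a minor one. It does not remove it: the error in the absolute rates has one direction and does not average out.

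**Never-use may be rare or nil.** A reader might take Protocol 13.1, which mentions participants who end up not using the device, as evidence that never-starters are expected. That section concerns discontinuation, and stopping after some use fits it equally well. It gives plausibility at most and no rate. Protocol 10.5 classes some consented people who receive no study intervention as screen failures, which could be read to remove some non-starters. But it too turns on receipt, and it does not redefine mITT.

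**Not every safety result is affected.** A reader might infer that the whole safety section is diluted, cybersickness included. Event counts have no denominator. Cybersickness is also measured by the weekly VR Sickness Questionnaire, for which the SAP sets no analysis or denominator. The dilution is shown only for per-subject AE incidence.

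**The comparison with Sham.** A reader might infer that the plan tilts this comparison towards the device. The documents do not support that. Participants are blinded, both groups get the same headset, and a never-starter has not seen the content, so there is no evident reason for never-use to differ by arm. If it did, the ratio could move in either direction.

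**Conclusion.** The mismatch is real and explicit in the text. SAP 1.8.2 and 3.2 count recipients; Protocol 16 and 16.4 observe wearers. Each per-subject AE incidence is multiplied by (1 - u).

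The documents do not determine the size. Over an assumed u of 1% to 15% the relative understatement is 1% to 15%, and it is zero if every recipient wears the headset once. Only two effects have a known direction: the understatement of absolute per-subject incidence and, if never-use is equal in both arms, the shrinkage of the risk difference. The risk ratio is then unchanged. A claim of bias in favour of the device in the between-arm comparison would need unequal never-use in a particular direction, for which the documents give no evidence.

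**What to change.** - In SAP 1.8, define a Safety Analysis Set: all participants who put the headset on at least once. Count a participant with no usage log as exposed unless that participant reports never having used it.
- In SAP 3.2, use this set for the per-subject tables and show the mITT-based rates as supportive.
- Report by arm the number of never-users and the number with unknown use, so that readers can judge u for themselves.
- Leave mITT unchanged for efficacy.

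**Cost.** The data are already planned: frequency and length of use are stored on the headset and sent remotely or read on return (Protocol 12.2 and 14.2). The logs must be linked to the AE data, which takes some work because Protocol 18.2 keeps the datasets under different participant identifiers. AE rates become slightly less favourable. The repair is incomplete: some headsets may not come back (Protocol 13.4), and never-users who have no log and cannot be reached remain in the denominator. The count of unknown use shows how much that could matter.

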1.8.3 PER PROTOCOL ANALYSIS SET (PP)

The primary endpoint and selected secondary endpoints will be repeated in the Per Protocol (PP) Analysis Set. The PP analysis set will exclude from the mITT analysis set subjects who did not receive a device, who have clinically significant violations of inclusion or exclusion criteria or who have post-treatment protocol violations that may reasonably be predicted to impact on effectiveness endpoints. For the purpose of defining this analysis set, treatment compliance is defined as using the device at least 42% within 8 weeks of treatment. Subjects using the device less than 42% will be excluded from this Analysis Set. Consistency with the mITT analysis will be evaluated and described in the Clinical Study Report.

1.8.4 COMPLETERS ANALYSIS SET (CC)

The primary endpoint and selected secondary endpoints will be repeated among those subjects completing the 56 days of treatment and have their final follow-up evaluation (“8-week outcome”.) The CC analysis set will exclude from the mITT analysis set subjects who are missing their primary 8-week Pain evaluation. Consistency with the mITT analysis will be evaluated and described in the Clinical Study Report.

1.8.5 MATCHED ANALYSIS SET (MAS)

A Matched Analysis Set (MAS) is defined and described in the standalone Health Care Economics Protocol drafted by the Sponsor.

1.8.6 TRAINING CASES (TC)

There are no training subjects for this protocol.

2 EFFICACY EFFECT ANALYSES

2.1 DESCRIPTIVE ANALYSIS

Observed values within the four (4) experimental groups and differences among groups in primary and secondary endpoints will be summarized using descriptive statistics, including means, standard deviations, medians, minimum, and maximum values for continuous data, and frequencies and percentages for categorical data. 95% Confidence or Credible Intervals will be provided for all analysis and provided with clinical interpretations in the Clinical Study Report. Graphical analyses of most variables will be provided with summary statistics including standard error or posterior interval markings.

2.2 PRIMARY ENDPOINT

The primary study endpoint is the change in absolute Pain Intensity **or** Pain Interference at 8 weeks post treatment from baseline (i.e., pre-treatment). Evaluation of the primary endpoint will utilize both EaseVRx (EaseVRx-8w and EaseVRx-8w plus extended on-demand library) and ShamVR (Sham VR-8w and ShamVR-8w plus extended on-demand library) arms with the two EaseVRx and two Sham VR groups being combined resulting in a two-group comparison. This is justified given that differences between the arms only occur after 8 weeks when primary endpoint data will be collected and locked in the database.

2.3 PRIMARY HYPOTHESIS

This trial contains multiple primary endpoints (MPE). Study success will be declared if at least one endpoint is statistically significant correcting for multiplicity.

The primary effectiveness hypothesis is superiority of the investigational device relative to control in terms of the mean improvements (or reduction) in Pain Intensity **or** Pain Interference from baseline to Week 8.

The primary null and alternative hypotheses of superiority may be represented symbolically as:

Ho: $\delta(\text{pain})_{\text{EaseVRx}k} - \delta(\text{pain})_{\text{Sham}k} \leq 0$, for all k

Ha: $\delta(\text{pain})_{\text{EaseVRx}k} - \delta(\text{pain})_{\text{Sham}k} > 0$, for at least one k

Where $\delta(\text{pain})_{\text{EaseVRx}k}$ and $\delta(\text{pain})_{\text{Sham}k}$ are the mean change (or reduction) from Baseline at Week 8 for EaseVRx and Sham, respectively. K indexes the two unordered Primary Endpoints, Pain Intensity and Pain Interference. When K is greater than 1, type 1 error increases. To control type 1 error, multiplicity adjustment is necessary and therefore is prespecified and described below.

2.4 TESTING THE PRIMARY SUPERIORITY HYPOTHESIS

Superiority testing will be performed using a mixed model for repeated measures (MMRM) analysis of covariance (ANCOVA) Model. The MMRM approach is a direct likelihood

approach requiring specialized statistical software. For this study, all MMRM parameters will be estimated using appropriate statistical software (see Software below). The MMRM model is notable for its inclusion of all available data from all eligible subjects and does not require their exclusion as in complete case analysis or arbitrary assignment of some value as in Last Observation Carried Forward (LOCF). Inclusion of outcome data from time points earlier than Week 8 informs the implicit imputation of missing Week 8 values through the covariance matrix used to model the random effects.

The random effects in an MMRM model are based on the so-called ‘unstructured covariance matrix’ in which variances over time are allowed to vary as are the pair-wise correlations over time.

The values over time include all Pain scores, namely at each and all of the 2x week follow-up time points through Week 8.

All Pain values will be included in the analysis even if they are obtained out-of-window. The fraction of out-of-window visits will be summarized at each time point.

The contrast indicated by the primary hypotheses above, $\delta(\text{pain})_{\text{EaseVRx}} - \delta(\text{pain})_{\text{sham}}$ will be estimated as the treatment group contrast from baseline to Week 8 in the Pain score derived from the MMRM. The null hypothesis is that the true value of this contrast is equal to zero. The same approach will be taken for testing both Pain Interference and Pain Intensity.

2.4.2 DETAILS OF THE MMRM

As stated above, the covariance matrix for MMRM is an unstructured covariance matrix in which each of the variances (at every follow-up) are free to vary as are the covariances.

That is, the covariance matrix for the MMRM will not include any random effects per se, but accounts for correlations among errors by specifying the form of the covariance matrix. The MMRM employs an unstructured covariance to produce inferences that are valid under the so-called ‘missing at random’ (MAR) assumption which is more generally true than the ‘missing completely at random’ assumption that is required for validity of analyses restricted to complete cases.

The longitudinal model will be specified as a repeated measures model that expresses the Pain score as a linear function of treatment, time, treatment-by-time interaction, and a covariate of the baseline pain measurement.

The model is mathematically expressed as:

$$\mathbf{Y}_i = \mathbf{X}_i \boldsymbol{\beta} + \mathbf{e}_i$$

Where:

- \mathbf{Y}_i is change from baseline to Week 8 in Pain
- $\boldsymbol{\beta}$ is a vector of fixed-effect regression parameters which includes:
 - o μ , the overall mean
 - o θ , the treatment effect
 - o τ , a vector of post-baseline time effects
 - o η , a vector of treatment-by-time interaction effects
 - o ϕ , a vector of covariate effect parameters that only includes baseline Pain score but in general could include additional baseline variable
- \mathbf{X} is a design matrix for the fixed effects, and
- \mathbf{e} is the error vector with
 - o $E(\mathbf{e}) = \mathbf{0}$ and
 - o $Var(\mathbf{e}) = \sigma_e^2 V_{unstructured}$

The specific model to be used may be expressed as:

$$\mathbf{Y} = \mathbf{b}_{int} + \mathbf{b}_{base} + \mathbf{b}_T + \mathbf{b}_1 + \dots + \mathbf{b}_{56} + \mathbf{b}_T \mathbf{b}_1 + \dots + \mathbf{b}_T \mathbf{b}_{56}$$

With parameters as explained below.

Parameter	Represents
Y	Change from baseline
b_{int}	Model intercept
b_{base}	Baseline value
b_T	Indicator for Active Treatment
b_1, \dots, b_{56}	Indicator for each timepoint, subscripts index categorical visit with 1 being the first day of treatment, and 56 being the final day of treatment.
$b_T b_1, \dots, b_T b_{56}$	Indicators allowing varying treatment differences at each timepoint

From this model estimates of treatment effect at specific visits and specifically at Week 8 difference may be obtained as follows.

$$T_{w8} = b_{int} + b_{base} + b_T + b_T b_{56}$$

$$S_{w8} = b_{int} + b_{base}$$

$$\Delta_{w8} = T_{56} - S_{56} = b_T + b_T b_{56}$$

Where T_{56} and S_{56} are the expected changes from baseline to Week 8 in the Pain scores in the active and sham control groups, respectively. In terms of these model parameters, the superiority hypotheses are:

$$H_0: \Delta_{w8} = 0; H_1: \Delta_{w8} > 0 \text{ when larger values reflect improvement or}$$

$$H_0: \Delta_{w8} = 0; H_1: \Delta_{w8} < 0 \text{ when smaller values reflect improvement}$$

2.5 TESTING THE SECONDARY ENDPOINTS

Analyses of secondary endpoints will focus on presenting between group differences and 95% confidence intervals from statistical models appropriate for the distribution of the endpoint of interest. For continuous endpoints with repeated measurements (e.g., Change in Pain scores at all timepoints post-dosing), analyses will be performed utilizing the MMRM approach as the primary analysis. The endpoints will also be evaluated using the Values over time adjusted for baseline differences approach as the primary analysis.

Endpoints assessed at a single timepoint will be compared using consistent approaches applied in the context of appropriate methods for cross-sectional data, including linear regression for continuous secondary endpoints.

Statistical significance for the following secondary endpoints will be determined based on a Hochberg step-up procedure (see below).

- ODI
- PROMIS sleep disturbance
- PROMIS anxiety
- PROMIS depression

All other endpoints may be provided with nominal p-values and reported as nominal in the Clinical study report and publications.

All secondary endpoints will include nominal 95% Confidence or Credible Intervals to allow for clinical interpretation in the Clinical Study Report. Analyses will be reported in both tabular and graphical form.

2.6 RESPONDER ANALYSIS JUSTIFICATION

If the study obtains success around the primary endpoint, we will conduct supplementary analysis to evaluate the sensitivity of these study results using supplemental responder analyses. Specifically, we will evaluate whether a greater portion of participants who received active treatment had clinically important differences (CIDs) compared to those in the sham arm. CID thresholds are commonly used to answer the question of whether statistically significant differences in groups are driven by meaningful improvements in individuals. Broadly, there are two classes of CIDs for evaluating change from baseline. One approach is based on percent change in score; the other is based on specified point change in score. We will conduct responder analyses using both approaches. The table below the responder definitions for each measure Brief Pain Inventory (BPI) Measure (Average Pain and Pain Interference) and each Supplementary Analysis.

Table 1: Responder Definition for Brief Pain Inventory Measures of Average Pain and Pain Interference

	Responder Analysis 1	Responder Analysis 2
BPI Average Pain	30% decrement in score compared to baseline	Decrease of 2 points on 0-10 scale (one item)
BPI Pain Interference	30% decrement in score compared to baseline	Decrease of 2-point on 0-10 (average of 7 items scored 0-10)

The choice of the above thresholds is based on research precedent and recommendations. Regarding the 30% threshold, the IMMPACT consensus statement concluded that changes of 30% to 36% represent ‘much better,’ ‘much improved,’ or ‘meaningful’ decreases in chronic pain”, p. 111 (Dworkin, 2008). With respect to single item numerical rating scales (NRS) such as BPI Average Pain, another relevant study was conducted by Farrar and colleagues (Farrar, 2000). They evaluated a range of percentage change thresholds for a 0-10 NRS: $\geq 10, 15, 25, 33, 40, 50, 60, 75.5$ and concluded that a threshold of 33% had the best balance of specificity, sensitivity, and accuracy. Subsequently, studies cited Farrar to support a 30% threshold, even though Farrar did not specifically evaluate a 30% threshold. However, on a 0-10-point scale, the point changes are identical with either a 30% or 33% threshold. Another study of relevance is one by Ostelo and colleagues conducted in the context of low back pain (Ostelo, 2005). This study concluded that a 23% change in NRS score was a reasonable threshold for a minimally clinically important change for patients with chronic

low back pain. A 30% criterion has been used for scores based on the Brief Pain Inventory (BPI) short form (Deere, 2021) and for the BPI Pain Interference subscale (Bomalaski, 2018). Another study used the 30% criterion for scores on the BPI Sleep Interference Scale (BPISI) scale (Mehta, 2016). A study in patients with fibromyalgia estimated a slightly higher CID threshold of 32.3% for BPI Average Pain (Meese, 2011, p. 824).

Studies exploring and applying point-based CID thresholds for BPI Average Pain and BPI Pain Interference typically use 1-2 points. Based on prior work, Krebs and colleagues estimated a 1-point CID threshold for both BPI Average Pain and Pain Interference (Krebs, 2010). They then used these estimates in a randomized clinical trial of pain function in patients with chronic back pain or hip or knee arthritis (Krebs, 2018). In contrast, Mease and colleagues estimated clinically important change in BPI Average Pain and BPI Interference scores in a sample of patients with fibromyalgia and derived a CID value for both measures of ≈ 2 score points (Mease, 2011).

Given the amount of evidence and precedence for the 30% criterion for measures of pain severity and interference including those of the BPI, we believe a 30% score change is an appropriate threshold for clinically meaningful change in scores. For the score point CID criterion, an improvement of either 1 or 2 points on the 11-point scales could be justified. We chose to go with the more stringent 2-point CID for both measures.

